## Synopsis

### EudraCT:

**Title:** Immediate versus delayed insertion of intrauterine contraception at the time of medical abortion- An open-label, randomized, multicenter study

- Aim** To study use, safety and patient acceptability of intrauterine contraception after immediate insertion compared with standard insertion 2-4 weeks post medical abortion at 3, 6 and 12 months post abortion.
- Drug:** Mirena® (LNG-IUS 52mg), Kyleena® (LNG-IUS 19.5mg), Jaydess® (LNG-IUS 13.5 mg), NovaT® (Cu-IUD, medical device, but due to use outside indication it is included in this application)
- Design:** Open label, randomized, controlled, multicenter study. Phase III (therapeutic confirming).
- Primary objective:** To study if immediate insertion of intrauterine contraception is superior to insertion at 2-4 weeks post abortion with regard to number of women using IUC as contraception at 6 months post abortion.
- Variable:** The proportion of women in each group (immediate or delayed) using IUC as contraception at 6 months post abortion (use vs non-use).
- Secondary objectives:** To study if immediate insertion of intrauterine contraception is non-inferior to delayed insertion with regard to safety and acceptability.

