### ***4.3 Secondary objectives***

The secondary objectives are to study if immediate insertion of IUC postpartum is non-inferior to golden standard (insertion 2-4 weeks postpartum) with regard to efficacy, safety and acceptability.

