#### **4.4.2 Safety:**

- Expulsion rate during 12 months following insertion in both groups evaluated by telephone follow up at 3, 6 and 12 months post abortion (complete, partial or no expulsion. The exact day of expulsion will be noted to determine the risk of expulsion as a function of time post insertion),
- Complications (adverse events (AE) and serious AE) bleeding requiring any treatment, uterine perforations and cervical tears, infection requiring treatment with antibiotics, hospitalization for any reason, surgical procedures due to heavy bleeding, incomplete abortions, prolonged bleeding or patient request,
- The proportion of surgical procedures in total and for each study site (type of procedure, reasons therefore- infection, retained products of conception, prolonged bleeding etc).

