## **5 Design**

The study protocol is designed as a superiority trial according to the recommendations in the CONSORT statement for randomized superiority trials ([www.consort-statement.org](http://www.consort-statement.org)). It is defined as a Phase III trial (therapeutic confirming).

The flow of patients is presented in this flowchart.

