## **17 Statistical considerations - Sample size**

### ***17.1 Justification of power calculation***

A total of 720 women will be recruited. In order to be able to show a difference of 80 percent in IUC usage in the immediate insertion group at 6 months post insertion compared to 60 percent use in the delayed group with a power of 90 percent and an alpha of 0.05 we would need to randomize 109 women in each group. If close to 100 percent of women receive the IUC in the immediate group and there is an expulsion rate of maximum 15 percent (immediate post placental insertion after delivery has expulsion rates of 15 percent) and some women have the IUC removed a use of approximately 80 percent could be expected in the immediate group. In the delayed group fewer women are estimated to come for insertion and the expulsion rate is estimated at 5 percent.

We will stratify women in three gestational age categories ( $\leq 9$  weeks+0 days, 9weeks +1 day  $\leq 12$  weeks+0 days, and  $>12$  weeks) to make study data more internationally applicable. We will compensate for surgical procedures due to incomplete abortions and prolonged bleeding which is estimated to be needed in approximately 3-5 percent (13). We will also compensate for a 15 percent loss to follow up which is commonly seen in studies in abortion. Thus, we will randomize 240 women in each gestational strata (total 720 women). Analysis will be presented as intention to treat for all randomized women as well as per protocol for women completing the 6 month follow up (see analysis plan). Follow up at 3, 6 and 12 months will be performed by telephone/email. In women who does not attend FU electronic patient records will be searched for main and secondary outcomes (safety, pregnancy, abortion).

- Primary outcome:

The primary outcome is the difference in women with IUC use at 6 months between the two groups (immediate and delayed insertion). The results will be analyzed by Fisher's exact test. A sensitivity analysis will be performed using logistic regression taking center, parity and age into account.

- Analysis populations

The main analysis population for primary outcome will be a modified intention to treat (mITT). This population is all randomized women, with medical abortion, and follow up for main outcome recorded at 6 months. Hence, also women with no insertion and women experiencing expulsion are included in this mITT.

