A sensitivity analysis will be performed on a strict ITT-population consisting of all randomized women having had medical abortion. In this analysis it is required to impute the outcome for women lost to follow up.

- Secondary efficacy outcomes:

1. Abortion rate as difference in proportion of individuals in each group at 3, 6 and 12 months,

Since both the primary outcome and this outcome involve data from different time-points several tests can be performed. In order to reduce the risk for type-I error each research question will be addressed with a global test including all available time-points first, before studying individual time-points. The data has a repeated-measure structure with a dichotomous outcome and most likely more observations available for early time-point compared to later time-points. To properly handle this data-structure we will use a multivariate permutation test based on a Fisher's combination function of individual  $p$ -values from time-specific tests (Fisher's exact test). If this global test is non-significant no individual time-points will be considered significant

2. Difference in the proportion of women who successfully have the IUC inserted (success versus failure),

Analyzed by Fisher's exact test.

- Secondary safety outcomes

1. rate of complications such as expulsions, perforations, infections. (Fisher's exact test)
2. Length of post abortion bleeding (difference in mean number of days in groups and per IUC use (hormonal/copper). Analyzed by T-test or Mann-Whitney U-test depending on the observed distribution (normal or skewed).
3. Pain at insertion on a VAS. Analyzed by Student's t-test

These secondary analyses concern safety where it is not sensible to adjust for multiple testing. The adjustments (with e.g. Bonferroni) increases the risk for type-II errors. As safety issues are very important we do not wish to increase the risk for type-II errors. Moreover, the analyses are listed under secondary endpoints so this implies that the results should be interpreted with more caution compared to the primary result.

- Secondary acceptability outcomes
  1. preferred method: immediate or delayed and if they would recommend their timing of insertion to a friend (yes/no). Analyzed by multivariate logistic regression with group, demographic variables and type of IUC (hormonal/copper) as explanatory variables.

Secondary analyses will be performed on all women with available data.

- Interim analysis:

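### The secondary objective is non-inferiority on safety and acceptability, but section 17.1 fixes only tests of difference, with no margin, so the planned analyses cannot establish it

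*Protocol*

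**What the plan says.** The protocol states the secondary objective twice, in different terms.

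- Synopsis, Secondary objectives: "To study if immediate insertion of intrauterine contraception is non-inferior to delayed insertion with regard to safety and acceptability".
- Section 4.3: immediate insertion is to be shown "non-inferior to golden standard (insertion 2-4 weeks postpartum) with regard to efficacy, safety and acceptability". This version adds efficacy and names a postpartum setting.

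Section 5 describes the trial in one framework only: "The study protocol is designed as a superiority trial according to the recommendations in the CONSORT statement for randomized superiority trials".

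Section 17.1 assigns the analyses. The first safety outcome is the "rate of complications such as expulsions, perforations, infections", with Fisher's exact test. Length of bleeding gets a t-test or Mann-Whitney test, pain at insertion a Student's t-test, and acceptability a logistic regression on group, demographic variables and type of device. All tests are at the 5% level.

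Expulsion is the first safety variable in section 4.4.2: "Expulsion rate during 12 months following insertion in both groups evaluated by telephone follow up at 3, 6 and 12 months post abortion". The power justification allows at most 15% expulsion after immediate insertion. For the other arm it says: "In the delayed group fewer women are estimated to come for insertion and the expulsion rate is estimated at 5 percent".

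**The concern.** Non-inferiority is a claim that any disadvantage is smaller than a stated amount. It needs that amount (the margin) and a rule, usually that the confidence limit lies inside it. A test of no difference asks something else. When events are few it will often be non-significant whether or not there is real harm.

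Section 5 asks as a research question whether immediate insertion can be done with safety and acceptability maintained. If the only evidence is a set of difference tests, a positive answer would rest on an absence of significance, and the less common the complication, the more easily that absence arises. This matters in a Phase III trial that is meant to inform guidelines on device insertion after medical abortion.

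**Working it through.** **1. The plan's own sample size.** The only calculation in the protocol is for the primary superiority comparison: 80% vs 60%, 90% power, alpha 0.05. With pooled variance, two-sided and no continuity correction:

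n = [1.960 × √(2 × 0.70 × 0.30) + 1.282 × √(0.80 × 0.20 + 0.60 × 0.40)]² / 0.20² = 108.2, rounded up to 109 per group.

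This reproduces the stated 109. No calculation for non-inferiority appears.

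**2. Is there a margin anywhere?** Two figures could be mistaken for one.

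- The 20-point difference in section 5 is the clinically relevant difference for the primary outcome, under superiority.
- The limits of 20% expulsion and 50% acceptability in sections 5 and 12.5 are interim stopping limits on rates. They do not bound a difference between arms.

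Neither serves as a non-inferiority margin for safety or acceptability.

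**3. What a non-significant Fisher test would mean.** Inputs: 720 women at 1:1 give 360 per arm; with the protocol's 15% loss, 360 × 0.85 = 306 per arm. The protocol gives no complication rates by arm, so the rates below are assumptions. Power is the exact sum of binomial probabilities over all tables with two-sided Fisher p ≤ 0.05.

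| Assumed true rates | 360 per arm | 306 per arm |
|---|---|---|
| 4% vs 2% | 28% | 23% |
| 2% vs 1% | 12% | 9% |

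A doubling from 2% to 4% would therefore give no significant difference in about 72% (360 per arm) to 77% (306 per arm) of trials. A doubling from 1% to 2% would do so in about 88 to 91%.

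**4. Expulsion.** Inputs: 15% (the protocol's maximum) vs 5%. Assume 306 immediate insertions (close to all women followed) and 200 delayed. As a check on the 200: 60% use and 5% expulsion imply 0.60 / 0.95 = 63% inserted if nobody has the device removed, and 306 × 0.63 ≈ 193.

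SE = √(0.15 × 0.85 / 306 + 0.05 × 0.95 / 200) = 0.0256

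95% CI = 0.10 ± 1.96 × 0.0256 = +5.0 to +15.0 points; 193 delayed insertions give the same limits to one decimal.

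The result depends on the true immediate rate and on a margin that the protocol does not state. Chance of meeting an assumed 10-point margin, with 5% in the delayed arm, 306 and 200 insertions, and one-sided 0.025, from Φ[(0.10 − d)/SE − 1.96], where d is the true difference and SE is recomputed at each rate:

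| True immediate rate | Chance of meeting 10 points |
|---|---|
| 6% | 99% |
| 8% | 89% |
| 10% | 58% |
| 15% | 2.5% |

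At 15% vs 5% with the same numbers, a 15-point margin would be met about 50% of the time and a 20-point margin about 97%.

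**The case against.** The strongest defence is that *non-inferior* is loose wording. Sections 5 and 17.1 treat the trial as a superiority trial, and no sentence says that p > 0.05 will be read as equal safety. Section 17.1 shows awareness of low power: it declines multiplicity adjustment for safety so as not to raise the type II error, and it asks for caution with secondary results. Confidence intervals could also be specified in an analysis plan that is not at hand.

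Part of this stands. The misuse is a risk and not a stated intention, and interval reporting may well sit elsewhere. But the protocol itself states the objective in two places and itself names the tests. Those two do not fit, and leaving out a multiplicity adjustment does not turn a difference test into a non-inferiority test.

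A reader might go further and infer that the protocol assumes threefold expulsion with immediate insertion, so that the objective is false by design. The documents do not support that. The 15% is a ceiling borrowed from insertion after delivery and used to justify about 80% use. Section 2 expects at most a slightly higher rate, and section 3.2 leaves the direction open. With no margin stated, the objective cannot be called false in advance.

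**Conclusion.** The objective and the analyses do not match. The synopsis and section 4.3 ask for non-inferiority; section 17.1 supplies tests that cannot establish it, and nothing in the protocol fills the gap. This rests on the text alone.

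The size rests on assumed complication rates. For a doubling from 2% to 4%, roughly three trials in four would show no significant difference under the planned test. For expulsion the problem is conditional: only near the 15% ceiling, and for a margin of 10 points or less, would non-inferiority be out of reach. For acceptability the defect is the missing margin and decision rule; the expulsion figures do not bear on it.

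Section 4.3 adds two smaller faults. It places the comparison postpartum, although the population is post abortion throughout the rest of the plan. It also puts efficacy under non-inferiority, although the design is superiority. The primary comparison and its sample size are not affected.

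**What to change.** 1. In the synopsis and section 4.3, reword the secondary objective as a comparison of safety and acceptability between the arms.
2. In section 17.1, report each safety and acceptability outcome as a risk or mean difference with a two-sided 95% confidence interval, and state that no conclusion of non-inferiority or maintained safety will be drawn from p > 0.05.
3. If any non-inferiority claim is kept, name the outcome and analysis population, fix and justify the margin before comparative data are seen, and decide by the confidence limit. Expulsion need not be excluded, but the margin should be chosen with the figures above in view.
4. In section 4.3, change *postpartum* to *post abortion*. Do not simply delete efficacy: insertion success and use at 3 and 12 months would then have no objective. Give them a comparative objective consistent with the superiority design.

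The cost is wording and added intervals. Treatment, recruitment and data collection do not change. The trial gives up only a claim that the named tests could not have supported.

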**Variables:**

**Efficacy, acceptability:**

- Use of IUC at 3, 6 and 12 months post insertion evaluated by telephone or e-mail follow-up (continued use/voluntary discontinued use, involuntary discontinued use including expulsions etc) reasons for discontinuation will be recorded and subsequent use of other contraceptive methods will be noted)
- Difference in the proportion of women who successfully have the IUC inserted (success versus failure),
- Ease of insertion according to health care provider (judged as very easy, easy, moderately, or very difficult)
- pain at time of insertion (women will indicate the pain before insertion, at placement of tenaculum, sound and IUC by putting a vertical mark on a 10 cm long horizontal line with a Visual Analogue Scale (VAS) from 0, indicating no pain to 10 indicating worst imaginable pain. Result will be noted in millimeters and entered into case report forms).
- Post-abortion bleeding (number of days of fresh bleeding and spotting after the abortion)
- Reasons for non-attempted insertion of IUC (change of mind, heavy bleeding, not coming for insertion, staff being unavailable etc),
- Pregnancies occurring during the 6 and 12 month follow-up (planned and unplanned, wanted and unwanted, pregnancy outcomes- ectopic, miscarriage, abortion, molar, kept pregnancy),
- Acceptability of immediate and delayed insertion of IUC by asking women if they would recommend the procedure to a friend (yes/no, asked at the time of insertion and at the 3 and 6 month follow up),
- Acceptability of IUC as post abortion contraception- evaluated as above,

**Safety:**

- Expulsion rate during 12 months following insertion in both groups evaluated by telephone follow up at 3, 6 and 12 months post abortion (complete, partial or no expulsion. The exact day of expulsion will be noted to determine the risk of expulsion as a function of time post insertion),
- Complications (adverse events (AE) and serious AE) bleeding requiring any treatment, uterine perforations and cervical tears, infection requiring treatment with antibiotics, hospitalization for any reason, surgical procedures due to heavy bleeding, incomplete abortions, prolonged bleeding or patient request,
- The proportion of surgical procedures in total and for each study site (type of procedure, reasons therefore- infection, retained products of conception, prolonged bleeding etc).

**PICO:**

**Population:**

Women with unwanted pregnancy having a medical abortion and fulfilling inclusion and without exclusion criteria and opting for IUC as post abortion contraception. The medical abortion will be carried out according to the Swedish national evidence based guidelines.

**Intervention:**

Randomized to insertion of IUC within 48 hours after medical abortion.

**Control:**

Randomized to insertion of IUC at the time of a follow-up visit scheduled 2 to 4 weeks after the abortion according to routine care.

**Objectives:**

Evaluation of use of IUC, feasibility, safety, compliance, and acceptability of immediate insertion of IUC 0 to 48 hours after medical abortion compared with delayed IUC insertion at 2 to 4 weeks post abortion. The primary outcome measure will be the use of IUC at 6 months in both groups evaluated by telephone calls/emails follow up.

**Time plan:** Planning: -March 2018  
Study start: May 2018  
End of recruitment: April 2020  
Last patient Last visit April 2021  
Analysis: 2022  
Report of primary outcome and Safety: 2021

### **Abbreviations**

LARC Long Acting Reversible contraception  
IUC Intrauterine contraception  
Cu-IUD Copper Intra Uterine Device  
LNG-IUS Levonorgestrel Intra Uterine System (levonorgestrel releasing IUC)  
LMV/MPA Läkemedelsverket/Medical Products Agency  
RERB regional Ethical Review Board

## **1 Protocol Summary**

The overall aim of this study is to increase use of intrauterine contraception (IUC) after medical abortion as IUC post abortion lowers rates of abortions and repeat abortions.(1-4) Our hypothesis is that immediate insertion of IUC after medical abortion results in higher use of IUC at six months post abortion compared to the current routine of delayed IUC insertion at 2-4 weeks post abortion.

Today 90 percent of terminations of pregnancy are medical abortions. Approximately 33 000 medical abortions are performed in Sweden each year and 20-30 percent of these women opt for IUC as post abortion contraception. Thus, the results of this study potentially affect at least 6600-9900 women every year in Sweden alone. A disadvantage with medical abortion compared with surgical abortion is the standard practice of delayed insertion of IUC. It has been shown that 42 percent of women scheduled for delayed insertion after surgical abortion did not return for the follow up and IUC insertion.(5) This problem is common also in medical abortion practice. Immediate insertion could lead to insertion rates close to 100 percent. However, this practice has not been studied for medical abortion.

The background for this trial is the belief that a higher rate of insertion of IUC, perhaps close to 100 percent, within 48 hours after medical abortion, can compensate more than well for a potentially higher rate of expulsion at immediate insertion. A clinically significant difference in IUC use at six months following the medical abortion of at least 20 percent is expected.

This large multicenter, randomized, patient centered clinical trial will investigate the effectiveness, feasibility, continued use, safety and acceptability of immediate insertion of intrauterine contraception within 0-48 hours after a completed medical abortion when compared to delayed IUC insertion at 2-4 weeks post abortion which is current practice.

## **2 Scientific background**

Sweden has the highest abortion rate in Western Europe. In Sweden approximately 33 000 medical abortions are performed every year ([www.sos.se](http://www.sos.se)) and 40 percent of all abortions are repeat abortions. Approximately 20-30 percent of women opt for intrauterine contraception

(IUC) post abortion. Results from several large retrospective and prospective studies from Finland, Scotland, USA and New Zealand show that use of long acting reversible contraceptive methods (LARC) such as implants and IUC lower the rate of abortions and repeat abortions.(1-4) IUC has the highest rate of user satisfaction and compliance among all contraceptive methods(3) and thus increased use benefits women as well as society.

Ovulation may return within one week of an abortion regardless whether it is medical or surgical. Therefore, immediate post abortion initiation of contraception is encouraged. In surgical abortion IUC is placed at the time of the surgery. Expulsion of an IUC inserted immediately following surgical abortion is rare (<6%).(6) There is no clear difference in the risk of expulsion, bleeding pattern, risk of infection or pain if the IUC is inserted at the time of the surgical abortion or if insertion is performed after 3 to 4 weeks. (5-7)

A disadvantage with medical abortion compared with surgical abortion is the delayed insertion of IUC, which is done at the follow up visit 2-4 weeks after the abortion treatment. It has been shown that 42 percent of women scheduled for delayed insertion after surgical abortion did not return for the follow up and IUC insertion. Among those who did return for a delayed IUC insertion a large proportion had already been exposed to risk of pregnancy. Studies show that a significantly higher proportion of women come for insertion of IUC post medical abortion if the insertion is performed at one week post abortion compared to insertion at the follow up visit scheduled at 2-4 weeks.(8) Provision of implants at the time of the medical abortion results in higher rate of use at 6 months following the treatment and a significantly lower risk of a subsequent unplanned pregnancy and abortion compared with insertion at 2 to 4 weeks post abortion.(9)

Post partum is also a sensitive period for unplanned and unwanted pregnancy. Insertion of IUC immediately after placental expulsion in childbirth results in lower rates of expulsion compared to insertion after 48 hours. Expulsion at immediate insertion post partum has been estimated at 15 percent.(10) The expulsion rate of IUC at delayed insertion has been shown to be 5 percent.(6) The approach of immediate IUC insertion post medical abortion has not been explored. There have been concerns that immediate post medical abortion IUC insertion may increase IUC expulsions due to bleeding and contractions or increase the risk of infection.

Our previous studies on the development of medical abortion, reduction of the number of visits for abortion and increased access to safe abortion through simplified medical abortion have had great impact on implementation and guidelines in Sweden and worldwide (11-13). However, there is an urgent need to update guidelines on post medical abortion IUC insertion where evidence based recommendations are lacking(14).

The rationale for this study is the hypothesis that a greater proportion of women undergoing medical abortion – close to 100 percent - will receive their intended post abortion IUC if it is inserted within 0-48 hours of the expulsion of the placenta compared with routine insertion at a scheduled follow up visit 2-4 weeks later. This could more than well compensate for a possible slightly higher rate of IUC expulsion and will reflect in a higher usage rate at 6 months following the abortion. If shown to be successful immediate IUC insertion will help women avoid subsequent unplanned and unwanted pregnancy following the abortion.

